8.3.2. Method of Detecting AEs and SAEs

The method of recording, evaluating, and assessing causality of AEs and SAEs, and the procedures for completing and transmitting SAE reports, are provided in Appendix 1, Section 11.1.

Care will be taken not to introduce bias when detecting AEs and/or SAEs. Open-ended and non-leading verbal questioning of the patient is the preferred method to inquire about AE occurrences. The investigator (or designee) is responsible for detecting, documenting, and recording events in addition to any reported by patients.

8.3.3. Follow-up of AEs and SAEs

After the initial AE/SAE report, the investigator is required to proactively follow each patient at subsequent visits/contacts. All SAEs will be followed until resolution, stabilization, the event is otherwise explained, or the patient is lost to follow up (as defined in Section 7.3). Further information on follow-up procedures is given in Appendix 1, Section 11.

8.3.4. Regulatory Reporting Requirements for SAEs

Prompt notification by the investigator to the Sponsor of an SAE is essential so that legal obligations and ethical responsibilities towards the safety of patients and the safety of a study intervention under clinical investigation are met.

The Sponsor has a legal responsibility to notify both the local regulatory authority and other regulatory agencies about the safety of a study intervention under clinical investigation. The Sponsor will comply with country-specific regulatory requirements relating to safety reporting to the regulatory authority, Institutional Review Boards (IRBs)/Independent Ethics Committees (IECs), and investigators.

Investigator safety reports must be prepared for suspected unexpected serious adverse reactions according to local regulatory requirements and Sponsor policy and forwarded to investigators, as necessary.

Confidential Page 47 of 74

An investigator who receives an investigator safety report describing an SAE or other specific safety information (e.g., summary or listing of SAEs) from the Sponsor will review and then file it along with the Investigator's Brochure and will notify the IRB/IEC, if appropriate according to local requirements.

8.3.5. Pregnancy

Pregnancy testing will be conducted as shown in the SoA (Table 1). Per the exclusion criteria, patients must not be pregnant or lactating, and per the inclusion criteria, sexually active patients must be willing to utilize one of the more effective birth control methods for 6 months after the T cell infusion. If a patient becomes pregnant during the study, they are to be discontinued from MT-401, but will continue follow-up (Section 7.1).

Details of all pregnancies in female patients and female partners of male patients will be collected after the start of MT-401 and until the Follow-up Visit.

If a pregnancy is reported, the investigator should inform the Sponsor within 24 hours of learning of the pregnancy and should follow the procedures outlined below.

Pregnancy outcomes will be collected and abnormal pregnancies (e.g., spontaneous abortion, fetal death, stillbirth, congenital anomalies, and ectopic pregnancy) are considered SAEs.

8.3.6. Adverse Events of Special Interest

No AEs of special interest are noted.

8.4. Treatment of Overdose

The dose of MT-401 is carefully monitored and administered by health care personnel. No overdose of MT-401 has been reported. In the event of an overdose, appropriate supportive treatment should be initiated according to the patient's clinical signs and symptoms.

8.5. Pharmacokinetics

Pharmacokinetic parameters are not evaluated in this study.

8.6. Pharmacodynamics

Pharmacodynamic parameters are not evaluated in this study, with the exception of biomarkers, as described in Section 8.8.

8.7. Genetics

Genetics are not evaluated in this study.

Confidential Page 48 of 74

8.8. Biomarkers

Collection of samples for other biomarker research is also part of this study including but not limited to blood and bone marrow biopsies/aspirate as noted in the Laboratory Manual. Samples for biomarker research are required and will be collected from all patients in this study as specified in the SoA (Table 1).

Samples will be tested for immune phenotype, repertoire and function, cell targeting, signaling pathways and disease status, including MRD to evaluate their association with the observed clinical responses to MT-401. If any previous local MRD testing has been completed, the results may be collected.

In addition, samples will be stored and analysis may be performed on biomarker variants thought to play a role in immune surveillance and function including, but not limited to, serum/plasma analytes, or tissue biomarkers to evaluate their association with observed clinical responses to MT-401.

Other samples may be used for research to develop methods, assays, prognostics and/or companion diagnostics related to immune pathways, disease process and/or mechanism of action of MT-401.

Samples may be stored for a maximum of 10 years (or according to local regulations) following the last patient's last visit for the study at a facility selected by the Sponsor to enable further analysis of biomarker responses to MT-401.

Other Tissue: If the patient dies, an autopsy may be requested. If granted, tissue may be requested to assess presence of infused cells and assess tumor antigen expression profile.

Bilateral bone marrow aspirations and other biopsies: Samples of a previous bone marrow biopsy (or other aspirates or biopsies of tissues suspected to be infiltrated with tumor cells) or of additional biopsies performed while the patient is on study will be used to assess disease status, as well as specificity and functionality of bone marrow infiltrating T cells. For any additional bone marrow biopsy (any performed in addition to the protocol specified bone marrow biopsies) the patient has had performed while he/she is on study, an extra 5-20cc of bone marrow aspirate and/or core biopsy will be obtained for the testing described above and provided to the Sponsor.

8.9. Medical Resource Utilization and Health Economics

Health Economics/Medical Resource Utilization and Health Economics parameters are not evaluated in this study.

8.10. Patient-reported Outcomes

As an exploratory endpoint (For Phase 2, Group 2 Subgroup C only), a PRO questionnaire will be completed. Additional details regarding the PRO questionnaire and associated instructions will be provided in a separate document.

Confidential Page 49 of 74

9. STATISTICAL CONSIDERATIONS

9.1. Sample Size Determination

9.1.1. Adjuvant Population (Group 1)

A total of approximately 150 Group 1 patients will be randomized with a 1:1 allocation to receive MT-401 or to be under observation (SoC arm). Median RFS for the SoC arm is expected to be approximately 8 months (Rashidi et al, 2016; Goyal, 2016). A clinically meaningful increase in median RFS for the MT-401 arm over SoC is thought to be 2 months or more. The primary analysis will be conducted when 90 RFS events have been observed. Ninety (90) RFS events provides 80% power with alpha=0.05 to detect a median RFS improvement of 6.5 months over the assumed SoC median RFS of 8 months (hazard ratio=0.55). Ninety RFS will be observed assuming uniform accrual of 150 patients (75 per arm) over a 50-month period and an additional 12-month minimum follow-up period. The DMC and Sponsor will review data from Phase 2 based on the planned interim analyses described in Section 9.5.

If the decision is made to dose patients in Phase 2 with any of the MT-401 dosing regimens evaluated in Cohorts III-V, enrollment will continue in Phase 2 Group 1 to achieve 150 evaluable patients randomized and approximately 75 patients treated with the final MT-401 dose and the intended manufacturing process, thereby replacing any patients that have not been treated with the final Phase 2 product, as determined by the Sponsor.

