Safety Lead-in (Cohorts I and II) and Cohorts III-V: Safety data will be reviewed at the end of the Safety Lead-in to determine if it is appropriate to move forward with the specific peptide manufacturer in the Phase 2 portion of the study. The evaluation of DLTs will be conducted in the DLT-evaluable set. Safety data will also be reviewed at the end of Cohort III to determine if it is appropriate to switch to a higher dose in the Phase 2 portion of the study. Additionally, safety data will also be reviewed at the end of Cohorts IV-V to determine if it is appropriate to switch to a dosing regimen with the MT-401 product manufactured using the accelerated process in the Phase 2 portion of the study. This decision will be made by the Sponsor based on multiple parameters, including the safety and biomarker data available.

One interim and 1 primary analysis are planned for Phase 2 Group 1. These analyses will be event driven and will occur when approximately 45 and 90 RFS events have been observed, respectively. The Data Monitoring Committee (DMC) will review safety and efficacy data at the interim analyses.

One interim analysis and 1 primary analysis is planned for Phase 2 Group 2. The interim analysis will occur after the first 10 patients per subgroup in Group 2 have completed their efficacy assessments and have had the opportunity to be followed for 6 months. The primary analysis will occur after all patients treated have been followed for 6 months.

The primary analysis of the study will occur when 90 RFS events have occurred in Phase 2 Group 1. The clinical study report will be written based on this analysis. If the primary analysis of either Group 1 or 2 occurs after the primary analysis of the other group, an addendum to the CSR will be written to describe the results of the other group.

General Methods of Analysis:

Confidential Page 15 of 74

Categorical variables will be summarized as counts and percentages. Continuous variables will be summarized with univariate statistics, including mean, median, range, and standard deviation. Confidence intervals (CIs) will be calculated for summary statistics, addressing the primary and secondary efficacy outcomes.

Safety Lead-In (Cohorts I and II) and Cohorts III-V:

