For both the Sa fety Lead-in, which includes Cohorts I and II, and Cohorts III-V, the number of DLTs per cohort will be identified. The confirmed dose and peptide manufacturer will be identified based on the procedures of the standard 3+3 design. Sa fety a nalyses described below for the Phase 2 portion of the study will also be conducted for the Safety Lead-in portion of the study and Cohorts III-V.

Secondary analyses (efficacy):

Phase 2:

Primary efficacy analyses: RFS curves will be estimated using the Kaplan-Meier (KM) product limit method. For Group 1, the hazard ratio and corresponding 95% CI will be estimated using a Cox proportional hazards model using randomized arm as a single factor. The KM estimate of the medians will be reported, and the corresponding 95% CI will be computed. KM estimates of RFS rates at milestone time points will be reported a long with two-sided 95% CIs using Greenwood's formula, provided the minimum follow-up in patients exceeds the time point to support stable estimation of the rate. In addition to the Cox model, a log-rank test will be used to compare the treatment arms stratified by pre-transplant MRD status (MRD+ vs. MRD-/Unknown) and cytogenetic risk (Unfavorable vs. Other).

For Group 2, the CR rate and the corresponding 95% exact CI will be calculated. The DOCR will be estimated using the KM product limit method. The DOCR will be estimated using the KM product limit method. The KM estimate of the median DOCR and the DOCR rates at milestone timepoints will be reported a long with the two-sided 95% CI.

Best overall response will be summarized by response category.

[figure not shown]
Safety Analysis: Safety and toxicity outcomes including treatment-emergent AEs, cytokine release syndrome (CRS), GVHD, neurological findings, and laboratory evaluations will be summarized using descriptive statistics for all patients in the All treated population by group. Safety evaluations will be based on the incidence, intensity, and type of AEs or serious adverse events (SAEs), as well as changes in the patient's physical examination findings, vital signs, and clinical laboratory results.

AEs will be assessed for severity according to the U.S. NCI CTCAE, Version 5.0,

Confidential Page 16 of 74

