2.2. Background

2.2.1. Acute Myeloid Leukemia

AML is a malignant neoplasm of myeloid lineage cells arising within the bone marrow and outgrowing normal hematopoietic elements. Although AML can present at all ages, it has a bimodal age distribution, with one peak within the first 10 years of life and a much larger peak beyond age 60. In 2019, there was an estimated 61,780 new cases of leukemia in the United States and 22,840 deaths from leukemia (all types), and 21,450 new cases of AML with 10,920 deaths (Key Statistics for AML, 2019).

Adult patients with AML are stratified based on cytogenetics and molecular features into low-, intermediate- and high-risk disease groups, in order to identify those who would benefit from allogeneic HSCT in first remission. The standard first-line treatment approach for the past 4 decades, regardless of risk stratification, has been combination chemotherapy using cytarabine and an anthracycline, which has produced initial complete remission (CR) rates in 50-80% of patients; however, approximately half of these patients eventually relapse. Eligible patients subsequently proceed to allogeneic HSCT, but disease relapse is frequent (~60%) and is a major cause of death in these patients (Estey and Döhner, 2006). Overall, patients who are not cured with front- or second-line therapy have an estimated median survival of <1 year (Estey and Döhner, 2006) highlighting the need for novel therapies. Pediatric patients are similarly risk stratified with disease response, as well as molecular features and cytogenetics being critical to assessment of prognosis. With improved therapy as well as supportive care, pediatric patients have ~70% chance of survival at 5 years from diagnosis; however, patients with refractory or relapsed disease (~35%) have a very poor prognosis. This subset is generally offered re-induction chemotherapy followed by allogeneic HSCT. Outcomes are improved with disease remission at the time of transplant, but overall survival in this group remains < 30% (Rubnitz, 2012).

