9.3. Statistical Analyses

The SAP will be finalized before database lock and will describe the patient populations to be included in the analyses, and procedures for accounting for missing, unused, and spurious data. This section is a summary of the planned statistical analyses of the primary and secondary endpoints.

The primary analysis of the study will occur when 90 RFS events have occurred in Phase 2 Group 1. The clinical study report will be written based on this analysis. If the primary analysis of either Group 1 or 2 occurs after the primary analysis of the other group, an addendum to the CSR will be written to describe the results of the other group.

Categorical variables will be summarized as counts and percentages. Continuous variables will be summarized with univariate statistics, including mean, median, range, and standard deviation. Confidence intervals (CIs) will be calculated for summary statistics, addressing the primary and secondary efficacy outcomes.

The primary analysis will include disease assessments associated with the first treatment regimen of MT-401 only. Any disease outcomes collected subsequent to re-treatment (i.e. re-dosing) will be analyzed separately.

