9.5. Interim Analyses

Safety Lead-in (Cohorts I and II) and Cohorts III-V: Safety data will be reviewed at the end of the Safety Lead-in to determine if it is appropriate to move forward with the specific peptide manufacturer in the Phase 2 portion of the study. The evaluation of DLTs will be conducted in the DLT-evaluable set. Safety data will also be reviewed at the end of Cohort III to determine if it is appropriate to switch to a higher dose in the Phase 2 portion of the study. Additionally, safety data will also be reviewed at the end of Cohorts IV and V to determine if it is appropriate to switch to a dosing regimen with the MT-401 product manufactured using the accelerated process in the Phase 2 portion of the study. This decision will be made by the Sponsor based on multiple parameters, including the safety and biomarker data available.

9.5.1. Phase 2 Group 1: One interim analysis is planned for Group 1.

The first interim analysis of Group 1 will occur when 45 RFS events have occurred in Group 1. It is anticipated that this will occur approximately 30 months after the first patient randomized. At this analysis, the DMC will assess safety, futility, and potential expansion of study accrual according to the criteria defined in the DMC charter. At the time of this analysis, enrollment of the remaining patients will continue, unless any safety concerns are identified.

9.5.2. Phase 2 Group 2:

After the first approximately 10 patients in each subgroup in Group 2 have progressed or had the opportunity to be followed for 6 months, clinical safety and efficacy will be reviewed comprehensively. Further enrollment for a subgroup may be terminated due to futility based on totality of the data. Patients

Confidential Page 57 of 74

treated in cohorts IV-V with the same manufacturing process as Group 2 may be included in Group 2 Subgroup C or Subgroup D analyses for decision making.

Details of the interim analysis will be described in the SAP, including pre-specified rules for futility and potential expansion of Group 1 enrollment and methods for control of the overall type I error rate.

Upon review of this interim analysis, the DMC may recommend adding additional patients to Group 2 based on the emerging data from the historical control study and the observed response rate at the interim analysis.

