The primary analysis of RFS will be performed when 90 RFS events have been observed. RFS curves will be estimated using the Kaplan-Meier (KM) product limit method. The KM estimate of the median, 25th and 75th percentiles will be reported, and their corresponding 95% CIs will be computed. KM estimates of RFS rates at milestone time points (ie, 3 month intervals) will be reported along with two-sided 95% CIs using Greenwood's formula, provided the minimum follow-up in patients exceeds the time point to support stable estimation of the rate. The hazard ratio and corresponding 95% CI will be estimated using a Cox proportional hazards model including a factor for randomized arm and stratification factors of pre-transplant MRD status (MRD⁺ vs. MRD⁻/Unknown) and cytogenetic risk (Unfavorable vs. Other). The treatment effect on RFS will be evaluated using a stratified log-rank test. The significance level to be used in the RFS analysis at the final analysis will be based on $\alpha=0.05$ (two-sided).

As noted in Section 7.4.2, if an imbalance of more than 20% between the MT-401 and SOC arms is observed among the age, genetic mutations, transplant donor type, conditioning regimen, or complete remission status prior to transplant, the primary analysis may be modified to stratify for these factors.

A landmark analysis will be performed including only patients who are relapse free, alive and have not withdrawn from the study by Day 0.

Phase 2 Active Disease (Group 2):

The CR rate and the corresponding 95% exact CI will be calculated. The number and percentages of patients in each best disease response category per ELN recommendations will also be presented. Results will be presented separately for Subgroups C and D. Data from a matched synthetic control arm may also be obtained and compared against the CR rate from Group 2 active disease patients as part of a separate statistical analysis plan.

The DOCR will be estimated using the KM product limit method and summarized similar to RFS as described above.

7.4.5 *Secondary Endpoint Analysis Methods*

Safety Lead-in (Cohorts I and II) and Cohorts III-V:

CR and DOCR will be summarized descriptively for active disease patients in the Safety Lead-in (Cohorts I and II) and Cohorts III-V similar to Group 2. Summaries will be presented by cohort and overall.

Phase 2 Adjuvant (Group 1):

The statistical methods for analyzing OS and GRFS for Group 1 patients are identical to those described for RFS.

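### Group 1's projection of 90 RFS events after 50 months' accrual plus 12 months' minimum follow-up does not follow from its stated inputs; with constant hazards and no loss they give about 128 events by then, and event 90 near month 45.

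*Protocol*

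**What the plan says.** Protocol 9.1.1 sets the Group 1 design values. "Median RFS for the SoC arm is expected to be approximately 8 months", and the target is an improvement of 6.5 months (hazard ratio 0.55) with 150 patients randomised 1:1. Ninety events are said to give 80% power at alpha 0.05, which SAP 7.6 specifies as two-sided. The next statement is the calendar projection: "Ninety RFS will be observed assuming uniform accrual of 150 patients (75 per arm) over a 50-month period", plus 12 months of minimum follow-up. SAP 7.6 carries the same sentence. Neither document attaches a loss rate, a plateau or a non-exponential RFS curve to it.

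The timing of the analysis is set by events. The synopsis says of the interim and primary analyses: "These analyses will be event driven and will occur when approximately 45 and 90 RFS events have been observed, respectively". Protocol 9.3 says: "The primary analysis of the study will occur when 90 RFS events have occurred in Phase 2 Group 1". SAP 7.4.7.3, Option 3, allows the event and accrual targets to rise at the interim if conditional power is between 50% and 80%; the event increase is capped at 50%. For the 45-event interim, protocol 9.5.1 forecasts: "It is anticipated that this will occur approximately 30 months after the first patient randomized".

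Minimum follow-up also governs one reporting rule. In SAP 7.4.4, "KM estimates of RFS rates at milestone time points (ie, 3 month intervals) will be reported", but there, in the synopsis and in protocol 9.3.2 this applies only "provided the minimum follow-up in patients exceeds the time point to support stable estimation of the rate".

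**The concern.** The projection names every input needed to check it, and 90 events looks low. By month 62 every patient has at least 12 months of follow-up, and the average is 12 + 25 = 37 months, against medians of 8 and 14.5 months. Far more than 60% of patients should have had an event by then.

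If event 90 comes much sooner, the primary analysis is triggered while patients are still being randomised, or shortly after. The 12 months of minimum follow-up is then a feature of the projection that the trial would not have. Milestone RFS rates at 3-month intervals depend on minimum follow-up, so, read literally, the reporting condition could exclude most of them. Sites, the DMC and the sponsor would also be planning around a date about 17 months too late (62 − 45).

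**Working it through.** **Inputs** (protocol 9.1.1, SAP 7.6): medians 8 and 8 + 6.5 = 14.5 months; 75 patients per arm; uniform accrual over 50 months, so 1.5 per arm per month; analysis point 50 + 12 = month 62 (this sum is mine and is not written in the documents). Constant hazards are assumed because the ratio of medians, 8/14.5 = 0.552, is the stated hazard ratio only under that model. Loss is first set to zero because none is stated.

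**1. The plan's own power figure.** Schoenfeld: power = Φ(√90/2 × |ln 0.552| − 1.96) = Φ(2.82 − 1.96) = 80.5%. The stated 80% reproduces.

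**2. Events at month 62.** Per arm, with λ = ln 2/median: E = 75 × [1 − (e^(−12λ) − e^(−62λ))/(50λ)].
- SoC, λ = 0.0866: 75 × [1 − (0.3536 − 0.0046)/4.332] = 69.0.
- MT-401, λ = 0.0478: 75 × [1 − (0.5635 − 0.0516)/2.390] = 58.9.
- Total 127.9, against 90 stated: 38 more, or 42%. In 20,000 simulated trials the 95% range was 119 to 136.

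**3. Month of event 90.** For t below 50, E(t) = 1.5 × [t − (1 − e^(−λt))/λ] per arm. At t = 44.9: SoC 50.4 + MT-401 39.6 = 90.0. By then 3 × 44.9, or about 135, patients are randomised. The simulated 95% range is months 40.4 to 48.7.

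**4. What would bring month 62 down to 90?** The loss rates and plateaus are assumptions, not document figures. Loss is exponential and independent at rate η = −ln(1 − annual loss)/12: λ becomes λ + η in the exponentials, and events are multiplied by λ/(λ + η). A plateau p uses S(t) = p + (1 − p)e^(−λt), with λ reset so that the medians stay at 8 and 14.5.

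| Assumption | Events at month 62 | Event 45, month | Event 90, month |
|---|---|---|---|
| No loss | 127.9 | 28.0 | 44.9 |
| 10% loss per year | 116.3 | 29.1 | 47.5 |
| 20% loss per year | 105.4 | 30.4 | 50.7 |
| 35% loss per year | 90.2 | 32.9 | 61.7 |
| Equal 20% plateau, no loss | 110.1 | 29.1 | 48.7 |
| Equal 30% plateau, no loss | 99.7 | 29.9 | 52.0 |
| Equal 38% plateau, no loss | 90.5 | 30.9 | 60.5 |
| 30% plateau + 15% loss per year | 90.3 | 31.7 | 61.4 |

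In simulation (4,000 runs each), event 90 came before accrual ended at month 50 in 99.6% of trials with no loss, 87% with 10% annual loss and 44% with 20%. It came before month 62 in 100%, 100% and 99.7%.

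**5. Cross-check on the interim.** The forecast of 45 events near month 30 fits the no-loss case (28.0) and also several of the cases that give 90 at month 62 (30.9 to 32.9). It does not show which assumption, if any, was used.

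**6. Minimum follow-up at event 90.** It is about zero with no loss or 10% annual loss, because accrual is still open, and 50.7 − 50 = 0.7 months with 20%. In the no-loss case about 35 SoC and 44 MT-401 patients are expected still to be at risk at 6 months, yet a rule based on the shortest follow-up would withhold the 6-month rate.

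**The case against.** The strongest defence is that the sentence claims sufficiency: this accrual and follow-up will yield the 90 events required. An expectation of 128 then satisfies it, and the plan is merely conservative. The wording allows that reading, but it does not rescue the 12 months. An analysis triggered at event 90 would be expected before accrual closes, so the stated minimum follow-up would not exist when the data are analysed.

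Second, the 90-event target is a default. Under SAP 7.4.7.3, Option 3, it can rise to as many as 135 (90 × 1.5), with more accrual. This stands, and the point is limited to the case where 90 is retained.

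Third, zero loss is an extreme. Protocol 9.3.2 (Table 9) and SAP 6.4.1.2 censor at new anti-cancer therapy and after extended gaps in assessment, so counted events will fall below the no-loss figure. That is right, but no rate is given, and 20% annual loss closes only 22.5 of the 38 events. Protocol 2.2.1 also says that "disease relapse is frequent (~60%) and is a major cause of death in these patients", and 60% of 150 is 90. The documents do not link that figure to the projection; it has no time horizon and covers relapse only, whereas RFS also counts deaths.

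Fourth, withholding milestone rates when follow-up is short is the purpose of the pre-specified condition. I accept this: the condition is clear and usable, and is not itself an error. The hazard ratio, log-rank test, Kaplan-Meier curves and medians are reported regardless.

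**Conclusion.** The projection does not follow from its stated inputs. With constant hazards and no loss, the expectation is about 128 events at month 62 rather than 90, with event 90 near month 45. Annual loss of 10 to 20% narrows the gap without closing it. With the 90-event target retained, the stated inputs do not deliver 12 months of minimum follow-up, and milestone RFS rates could be largely unreportable.

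Two stronger readings are tempting, and the documents support neither. A reader might infer that Group 1 is underpowered, but power depends on the event count and stays at about 80% under the constant hazard ratio. A reader might also infer that 12 months of follow-up is certain to be missed. It is likely under the stated inputs, but heavy loss, a plateau or an Option 3 increase could change that; the documents do not say what was assumed.

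Severity is minor: the error concerns timing and follow-up, not the validity of the primary test.

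**What to change.** Keep the 90-event trigger. In protocol 9.1.1 and SAP 7.6, replace the projection sentence with one that follows from stated RFS and loss assumptions. For example: with constant hazards (medians 8 and 14.5 months), uniform accrual of 150 patients over 50 months and no loss, the 90th RFS event is expected about 45 months after the first randomisation, with about 135 patients randomised; with 10 to 20% loss per year, at about months 47 to 51. Remove the 12-month minimum follow-up as a projected property unless the assumptions that deliver it are stated.

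If a plateau was assumed, state it for each arm and recheck the 80% power. Equal plateaus with these medians do not keep the hazard ratio at 0.55: simulated power at 90 events falls to 0.28 with a 30% plateau and 0.15 with 38%.

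The cost is one sentence in each document, and a stated follow-up that looks less favourable. The trigger, interim rules, patient numbers and milestone-reporting rule need no change.
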